3.4. Estimation of the annual standardized incidence rate and prevalence of AF patients

Table A12. Annual incidence rate of all AF patients between 2016 and 2019 (2020 for sensitivity analyses) in France

	2016			2017			2018			2019			2020*		
	N	Crude ¹	Standar dized ^{1,2}	N	Crude ¹	Standar dized ^{1,2}	N	Crude ¹	Standar dized ^{1,2}	N	Crude ¹	Standar dized ^{1,2}	N	Crude ¹	Standar dized ^{1,2}
Overall	xxx	x,x	x,x	xxx	x,x	x,x									
CI 95%		[x,x;x,x]	[x,x;x,x]		[x,x;x,x]	[x,x;x,x]									
Unexposed to OAC	xxx	x,x	x,x	xxx	x,x	x,x									
CI 95%		[x,x;x,x]	[x,x;x,x]		[x,x;x,x]	[x,x;x,x]									
Exposed to OAC³	xxx	x,x	x,x	xxx	x,x	x,x									
CI 95%		[x,x;x,x]	[x,x;x,x]		[x,x;x,x]	[x,x;x,x]									

AF : Non Valvular Atrial Fibrillation

¹Estimation are provided per 100,000 inhabitants

²Age-standardized using the French population as reference

Incidence rate will be stratified in the following subgroups: age groups (<80 years, 80-90 years, >90 years), active cancer, CAD, Modified CHAD₂DS₂VASC score strata, Stroke history, Having a malnutrition, Risk of falls, Frail patients, Morbid obesity, History of major bleeding, at least one visit to a nursing home, History of dementia, ACCI (categorical)

³Exposed to OAC if at least one treatment sequence for an OAC in a given year.

*For sensitivity analyses

Same table will be presented for sensitivity analyses:

- with 30 days and 90 days of maximal number of days allowed for being refilled
- with integration of all incident AF patient (i.e. inclusion of patients with an event of interest between inclusion date and index date)
- with AF patients identified only by LTD or hospitalization (new OAC users identified by the algorithm of Billonnet et al. not included)

Table A13. Annual prevalence of all AF patients between 2016 and 2019 (2020 for sensitivity analyses) in France

	2016		2017		2018		2019		2020*	
	N	Crude ¹	N	Crude ¹						
Overall	xxx	x,x	xxx	x,x	xxx	x,x	xxx	x,x	xxx	x,x
CI 95%		[x,x;x,x]		[x,x;x,x]		[x,x;x,x]		[x,x;x,x]		[x,x;x,x]
Unexposed to OAC	xxx	x,x	xxx	x,x	xxx	x,x	xxx	x,x	xxx	x,x
CI 95%		[x,x;x,x]		[x,x;x,x]		[x,x;x,x]		[x,x;x,x]		[x,x;x,x]
Exposed to OAC³	xxx	x,x	xxx	x,x	xxx	x,x	xxx	x,x	xxx	x,x
CI 95%		[x,x;x,x]		[x,x;x,x]		[x,x;x,x]		[x,x;x,x]		[x,x;x,x]

AF : Non Valvular Atrial Fibrillation

¹Estimation are provided per 100,000 inhabitants

Annual prevalence will be stratified in the following subgroups: age groups (<80 years, 80-90 years, >90 years), active cancer, CAD, Modified CHAD₂DS₂VASC score strata, Stroke history, Having a malnutrition, Risk of falls, Frail patients, Morbid obesity, History of major bleeding, At least one visit to a nursing home, History of dementia, ACCI (categorical)

³Exposed to OAC if at least one treatment sequence for an OAC in a given year.

*For sensitivity analyses

Same table will be presented for sensitivity analyses:

- with 30 days and 90 days of maximal number of days allowed for being refilled
- with integration of all incident AF patient (i.e. inclusion of patients with an event of interest between inclusion date and index date)
- with AF patients identified only by LTD or hospitalization (new OAC users identified by the algorithm of Billonnet et al. not included)

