9.1 Study Design

SIFNOS study is an observational retrospective cohort study using French national health insurance claims database (SNDS). A unique extraction of AF patients (exposed or unexposed to OAC therapy) in SNDS data will be used to conduct the study from 2016 to 2020.

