9.7.4.3 Estimation of the annual standardized incidence rate and prevalence

The analysis of annual standardized incidence rate and prevalence of diagnosed AF patients in France in 2016, 2017, 2018 and 2019 will be descriptive in nature and will be performed for each calendar year, from 2016 to 2020.

Prevalent and incident patients with an AF diagnosis will be the patients with a diagnosed NVAF during the historical period and the patients newly diagnosed AF during the inclusion period. The estimations of the prevalence and incidence of AF will be based on the count of patients living in France as denominator (based on socio-demographic data published by the National Institute for Statistics and Economic Studies (INSEE) and will be expressed per 100,000 inhabitants.

The analysis will include the following measures for summarizing the information on the prevalence and incidence of diagnosed AF patients, for each calendar year between 2016 and 2019 in France:

- Overall count of prevalent and incident of diagnosed AF patients in year Y, separately
- Overall crude prevalence and cumulative incidence of diagnosed AF patients in year Y, separately; computed as:

$$CP_Y = \frac{\text{count of prevalent diagnosed NVAF patients in year Y}}{\text{count of French adult residents from census data in year Y}} \times 100,000$$

- CP_Y represents the crude prevalence of diagnosed AF patients in the year Y
- Y represents the year of interest

$$CI_Y = \frac{\text{count of incident diagnosed NVAF patients in year Y}}{\text{count of patients at risk in year Y}} \times 100,000$$

- CI_Y represents the cumulative incidence of diagnosed NVAF patients in the year Y
- Y represents the year of interest
- *Count of patients at risk* represents French adult residents from census data in year Y minus count of prevalent diagnosed NVAF patients in year Y

- Overall age-standardized cumulative incidence of diagnosed AF patients in year Y computed as:

$$age - SCI_Y = \frac{\sum_i CI_{i,Y} \times N_{i,Y}}{\sum_i N_{i,Y}} \times 100,000$$

- $age - SCI_Y$ represents the age-standardized cumulative incidence of diagnosed AF patients in year Y
- i represents the age group (<65 years old / 65-74 / 75-79 / \geq 80 years)
- Y represents the year of interest
- $CI_{i,Y}$ represents the crude cumulative incidence of diagnosed AF patients in the age group i in the year Y

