- $N_{i,Y}$ represents the counts of patients at risk (French adult residents from census data in year Y minus count of prevalent diagnosed AF patients in year Y) in the age group i in the year Y

The estimations of the annual standardized incidence and annual prevalence of AF will be also performed according to exposure status (exposed to OAC or unexposed), every year. A patient will be considered exposed to OAC in a given year if the patient presents at least one sequence treatment for an OAC in the corresponding year.

9.7.4.4 Description of the use of oral anticoagulants (OACs) in AF incident patients initiating treatment (AF patients exposed to OAC therapy)

The analysis of the OAC treatment patterns will be descriptive and exploratory in nature.

The date of first reimbursement of any drugs of interest (VKA, apixaban, rivaroxaban, and dabigatran) will be considered as the regimen initiation date and mark the beginning of the identification of the treatment sequence (cf. table VII).

The duration of a prescription will be of 30 days for any drugs of interest. The grace period considered for any drugs of interest considered will be 60 days (30 days and 90 days will be considered for sensitivity analyses).

A treatment sequence will continue until one of the following occurs:

- A regimen switch, defined as the reimbursement of another OAC. The end date of the first treatment sequence is the day before the date of first reimbursement of another OAC.
- Discontinuation of drugs in the treatment sequence: if a period between two consecutive claims is superior to the duration of the treatment of the last claim, plus a permissible gap of at least 60 days (30 and 90 days for sensitivity analyses) then the medication is considered as stopped within the treatment sequence. The date of discontinuation (end date of the treatment sequence) will be fixed at the date of the last claim, plus the treatment duration of this last claim.
- End of follow-up.

The treatment pattern analysis will be providing the following information:

- Number and percentage of patients receiving each of OAC treatment during the follow-up
- Number and percentage of patients who received 1, 2, 3, 4 and 5+ sequence treatment during the follow-up
- Number and percentage of patients who have switched from an OAC to another during the follow-up

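### Tables A12 and A13 call for AF incidence and prevalence in 12 comorbidity or risk subgroups, but the plan has no denominator for them; the only written formulas give each subgroup's contribution to the national rate, not the rate within it

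*SAP*

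**What the plan says.** Secondary objective 4 is the annual incidence and prevalence of AF. SAP section 9.7.4.3 takes its denominators from published INSEE data; the estimates "will be based on the count of patients living in France as denominator".

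- Prevalence is divided by the "count of French adult residents from census data in year Y".
- For incidence, the count at risk "represents French adult residents from census data in year Y minus count of prevalent diagnosed NVAF patients in year Y".
- The only stratum-specific denominator serves age standardization, in the bands <65, 65-74, 75-79 and ≥80: adult residents "minus count of prevalent diagnosed AF patients in year Y) in the age group".

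The Table A12 footnote then states "Incidence rate will be stratified in the following subgroups: age groups (<80 years, 80-90 years, >90 years), active cancer, CAD". The list goes on to CHA2DS2-VASc stratum, stroke history, malnutrition, risk of falls, frailty, morbid obesity, major bleeding, nursing home visit, dementia and ACCI. That makes 12 variables besides age. Table A13 has the same list: "Annual prevalence will be stratified in the following subgroups: age groups (<80 years, 80-90 years, >90 years), active cancer, CAD". Both tables are expressed per 100,000 inhabitants. SAP Table XXI also lists CAD, frailty, active cancer and previous stroke as subgroups for this objective.

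On data, SAP section 9.1 says "A unique extraction of AF patients (exposed or unexposed to OAC therapy) in SNDS data will be used". SAP section 9.4.1 derives the stratification variables for patients selected into the study population. Protocol section 4.2.3 rules out matching to any other database.

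**The concern.** A rate stratified by CAD is normally read as the rate of AF among people with CAD. That needs the number of adults with CAD, and nothing in the plan supplies it. Most of the subgroup variables look back from an index date, which an adult without AF does not have, so the missing denominators are not even defined for people without AF.

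The programmer must either restrict the numerator to the subgroup and keep the census denominator, or improvise a denominator that the SAP does not specify. The first choice follows the written formulas. It yields the share of AF cases in the subgroup multiplied by the overall rate, printed under the name of a stratified rate. These would be national figures, and a reader could conclude that AF is rarer in people with a condition when it is more frequent in them.

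**Working it through.** **Inputs.** The documents state no subgroup rate and no subgroup denominator, so there is no figure of the plan's own to reproduce on this point. For illustration I use the 2018 standardized rate of newly treated AF, R = 410 per 100,000 (SAP section 7.1), which rests on 225,747 new users (SAP section 9.5). The population shares s and case shares c below are assumptions.

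**Scale check.** 225,747 / (410 / 100,000) = 55.06 million people. Assumed adult counts of 54, 55 and 56 million give 418, 410 and 403 per 100,000. On the 66 million persons that Protocol Appendix 1 gives for the whole database, the rate would be 342. Because 410 is standardized and the adult count is not stated, this shows only that 410 is on the scale of an adult population.

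**Formula.** Let D be the census denominator, A the AF cases, R = A/D, s the share of D in the subgroup and c the share of A in the subgroup.

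- Written formula with the numerator restricted to the subgroup: cA/D = c × R.
- Rate within the subgroup: cA/(sD) = (c/s) × R.
- Ratio of the second to the first: 1/s. This is exact for prevalence. For incidence it is exact if s is the share of the population at risk, and close if s is the share of all adults.

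**Results with R = 410.**

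| s (assumed) | c (assumed) | On whole denominator | Within subgroup | Factor |
|---|---|---|---|---|
| 2% | 10% | 41 | 2,050 | 50 |
| 5% | 20% | 82 | 1,640 | 20 |
| 10% | 30% | 123 | 1,230 | 10 |
| 30% | 60% | 246 | 820 | 3.3 |
| 60% | 10% | 41 | 68 | 1.7 |
| 95% | 80% | 328 | 345 | 1.05 |

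**Reversal.** Rows two and six are the two levels of one variable, say CAD at 5% of adults and 20% of AF cases. On the whole denominator the table prints 82 for CAD and 328 for no CAD, a ratio of 0.25; the two rows add up to the overall 410. Within the subgroups the rates are 410 × 0.20/0.05 = 1,640 and 410 × 0.80/0.95 = 345, a ratio of about 4.75. More generally, the rate within the subgroup exceeds that in its complement when c > s, while the printed row is the lower one when c < 0.5. The order is therefore reversed whenever s < c < 0.5, that is, for any condition more common in AF cases than in adults but held by fewer than half of the cases.

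**Standardized column of Table A12.** The formula in section 9.7.4.3 needs age-specific incidence and age-specific counts at risk. For a comorbidity row, both need adults at risk by age within the subgroup. Only the whole-population counts by age exist, so this column has the same gap.

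**The case against.** The strongest reply is that the SAP never says that subgroup counts are divided by all adults. The first formulas in section 9.7.4.3 are labelled as overall measures, and the SAP is silent on the denominator for the non-age subgroups. This stands: the whole-population reading is an inference from the only formulas given. The silence does not clear the plan, though, because no other denominator can be built from the planned data.

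A second reply is that the figure is legitimate as a measure of burden. The exposed and unexposed rows of the same tables already divide a subset of AF cases by the whole population. This also stands, provided the row is labelled so. Exposure as defined here classifies AF cases, so few readers would look for another denominator. CAD, cancer and dementia also occur in adults without AF, and there the word stratified invites the other reading. For CHA2DS2-VASc the rate within a stratum would need the score in people without AF, which the plan does not define.

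Third, the age rows are not free of trouble either: the formula's bands differ from the table's <80, 80-90 and >90. This is correct, but it can be repaired with census counts by age, whereas the other rows cannot.

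Finally, these strata cannot simply be deleted. Protocol sections 3.5.3 and 3.7.4 commit the analyses to stratification by CHA2DS2-VASc and by most of the listed conditions. This stands and shapes the fix.

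**Conclusion.** The point holds as an undefined denominator whose only written substitute does not give a stratum rate. The factor 1/s is arithmetic; the shares that give it a size are assumptions, since the documents contain none. On those shares it is 10 to 50 for conditions held by 2% to 10% of adults, about 3 at 30% and 1.05 at 95%.

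A reader might infer that the SAP prescribes division by all adults and that every non-age row would be far too low. The documents support neither. The first is not written anywhere, and the second fails for majority levels such as the absence of an uncommon condition, where the difference is slight. The objective is secondary and descriptive and carries no test, so no decision rule is affected. It should still be corrected before the tables are programmed, because the printed order of two levels can be the opposite of the true one.

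**What to change.** 1. In Tables A12 and A13, keep stratum rates per 100,000 for age only, and write census denominators for the table's own bands (<80, 80-90, >90). The first three bands of the existing formula sum to <80; splitting ≥80 needs finer INSEE counts.
2. For the 12 other variables, keep the stratification promised in the protocol, but report the number and percentage of incident (Table A12) or prevalent (Table A13) AF patients per year.
3. If a per-100,000 figure is kept for these variables, label it: *AF cases with the condition per 100,000 of the whole adult population, not a rate within the subgroup*.
4. Drop the standardized column of Table A12 for these rows.
5. Align Table XXI and both footnotes with this, and record the change against protocol sections 3.5.3 and 3.7.4.

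The cost is SAP wording, table shells and a short note on the protocol. No new data are needed: both tables already have a count column, and Tables A4 and A5 already describe most of these characteristics by year for incident patients.

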3.5. Description of OAC treatment patterns

Table A14. Description of OAC treatment pattern during the follow-up

	VKA		Apixaban		Dabigatran		Rivaroxaban		Overall	
	N	%	N	%	N	%	N	%	N	%
Sequence treatment										
Only 1	xx	xx.x								
At least 2	xx	xx.x								
At least 3	xx	xx.x								
At least 4	xx	xx.x								
At least 5	xx	xx.x								
Patients who switch from an OAC to another	xx	xx.x								
Treatment duration (months)										
Median	xx.x									
Q1 - Q3	xx.x- xx.x									
Min - Max	xx.x- xx.x									
Time to next treatment (months)										
Mean (std)	xx.x (xx.x)									
Median	xx.x									
Q1 - Q3	xx.x- xx.x									
Min - Max	xx.x- xx.x									

Patients with temporary or permanent discontinuation	xx	xx.x								
Type of delivery										
Hospital	xx	xx.x								
Private medical practice	xx	xx.x								
Prescriber's specialty										
Hospital-based physicians	xx	xx.x								
City cardiologist	xx	xx.x								
Generalist practitioners	xx	xx.x								
Other	xx	xx.x								
FIRST TREATMENT SEQUENCE										
Patients who switch from an OAC to another	xx	xx.x								
Patients with temporary or permanent discontinuation	xx	xx.x								
Patients with concomitant treatments	xx	xx.x								
Type of delivery										
Hospital	xx	xx.x								
Private medical practice	xx	xx.x								
Prescriber's specialty										
Hospital-based physicians	xx	xx.x								

City cardiologist	XX	XX.X								
Generalist practitioners	XX	XX.X								
Other	XX	XX.X								
SECOND TREATMENT										
SEQUENCE										
....	XX	XX.X								
THIRD TREATMENT SEQUENCE										
....	XX	XX.X								

Same table will be presented for sensitivity analyses with 30 days and 90 days of maximal number of days allowed for being refilled

Dabigatran Unexposed Dabigatran 3.69%

[figure not shown]

Figure A2. Example of sunburst for describing OAC treatment pattern

fictional example + Strata=Any OAC + Strata=VKA + Strata=Dabigatran + Strata=Rivaroxaban + Strata=Apixaban

[figure not shown]

Figure A3. Example of Kaplan Meier curves of persistence rate in months

3.6. HCRU and associated costs

Table A15. Description of HCRU and associated costs (including event related cost): <time period>

	Exposed to OAC			Unexposed to OAC	
	Apixaban (N=XXX)	Dabigatran (N=XXX)	Rivaroxaban (N=XXX)	VKAs (N=XXX)	All exposed (N=XXX)
HCRU (2016-2019)					
Total					
N (%)	xx (xx.x)	xx (xx.x)	xx (xx.x)	xx (xx.x)	xx (xx.x)
Mean (std)	xx.x (xx.x)	xx.x (xx.x)	xx.x (xx.x)	xx.x (xx.x)	xx.x (xx.x)
Median	xx.x	xx.x	xx.x	xx.x	xx.x
Q1 - Q3	xx.x - xx.x	xx.x - xx.x	xx.x - xx.x	xx.x - xx.x	xx.x - xx.x
Min - Max	xx.x - xx.x	xx.x - xx.x	xx.x - xx.x	xx.x - xx.x	xx.x - xx.x
Total (PPPM)					
N (%)	xx (xx.x)	xx (xx.x)	xx (xx.x)	xx (xx.x)	xx (xx.x)
Mean (std)	xx.x (xx.x)	xx.x (xx.x)	xx.x (xx.x)	xx.x (xx.x)	xx.x (xx.x)
Median	xx.x	xx.x	xx.x	xx.x	xx.x
Q1 - Q3	xx.x - xx.x	xx.x - xx.x	xx.x - xx.x	xx.x - xx.x	xx.x - xx.x
Min - Max	xx.x - xx.x	xx.x - xx.x	xx.x - xx.x	xx.x - xx.x	xx.x - xx.x
Hospital admission					
N (%)	xx (xx.x)	xx (xx.x)	xx (xx.x)	xx (xx.x)	xx (xx.x)
Mean (std)	xx.x (xx.x)	xx.x (xx.x)	xx.x (xx.x)	xx.x (xx.x)	xx.x (xx.x)
Median	xx.x	xx.x	xx.x	xx.x	xx.x
Q1 - Q3	xx.x - xx.x	xx.x - xx.x	xx.x - xx.x	xx.x - xx.x	xx.x - xx.x
Min - Max	xx.x - xx.x	xx.x - xx.x	xx.x - xx.x	xx.x - xx.x	xx.x - xx.x
Hospital admission (pppm)					
N (%)	xx (xx.x)	xx (xx.x)	xx (xx.x)	xx (xx.x)	xx (xx.x)
Mean (std)	xx.x (xx.x)	xx.x (xx.x)	xx.x (xx.x)	xx.x (xx.x)	xx.x (xx.x)
Median	xx.x	xx.x	xx.x	xx.x	xx.x
Q1 - Q3	xx.x - xx.x	xx.x - xx.x	xx.x - xx.x	xx.x - xx.x	xx.x - xx.x
Min - Max	xx.x - xx.x	xx.x - xx.x	xx.x - xx.x	xx.x - xx.x	xx.x - xx.x
Hospital at home					
N (%)	xx (xx.x)	xx (xx.x)	xx (xx.x)	xx (xx.x)	xx (xx.x)
Mean (std)	xx.x (xx.x)	xx.x (xx.x)	xx.x (xx.x)	xx.x (xx.x)	xx.x (xx.x)
Median	xx.x	xx.x	xx.x	xx.x	xx.x
Q1 - Q3	xx.x - xx.x	xx.x - xx.x	xx.x - xx.x	xx.x - xx.x	xx.x - xx.x
Min - Max	xx.x - xx.x	xx.x - xx.x	xx.x - xx.x	xx.x - xx.x	xx.x - xx.x

			Exposed to OAC		Unexposed to OAC
	Apixaban (N=XXX)	Dabigatran (N=XXX)	Rivaroxaban (N=XXX)	VKAs (N=XXX)	All exposed (N=XXX)
Hospital at home (pppm)					
N (%)	xx (xx.x)	xx (xx.x)	xx (xx.x)	xx (xx.x)	xx (xx.x)
Mean (std)	xx.x (xx.x)	xx.x (xx.x)	xx.x (xx.x)	xx.x (xx.x)	xx.x (xx.x)
Median	xx.x	xx.x	xx.x	xx.x	xx.x
Q1 - Q3	xx.x - xx.x	xx.x - xx.x	xx.x - xx.x	xx.x - xx.x	xx.x - xx.x
Min - Max	xx.x - xx.x	xx.x - xx.x	xx.x - xx.x	xx.x - xx.x	xx.x - xx.x
Palliative care					
N (%)	xx (xx.x)	xx (xx.x)	xx (xx.x)	xx (xx.x)	xx (xx.x)
Mean (std)	xx.x (xx.x)	xx.x (xx.x)	xx.x (xx.x)	xx.x (xx.x)	xx.x (xx.x)
Median	xx.x	xx.x	xx.x	xx.x	xx.x
Q1 - Q3	xx.x - xx.x	xx.x - xx.x	xx.x - xx.x	xx.x - xx.x	xx.x - xx.x
Min - Max	xx.x - xx.x	xx.x - xx.x	xx.x - xx.x	xx.x - xx.x	xx.x - xx.x
Palliative care (pppm)					
N (%)	xx (xx.x)	xx (xx.x)	xx (xx.x)	xx (xx.x)	xx (xx.x)
Mean (std)	xx.x (xx.x)	xx.x (xx.x)	xx.x (xx.x)	xx.x (xx.x)	xx.x (xx.x)
Median	xx.x	xx.x	xx.x	xx.x	xx.x
Q1 - Q3	xx.x - xx.x	xx.x - xx.x	xx.x - xx.x	xx.x - xx.x	xx.x - xx.x
Min - Max	xx.x - xx.x	xx.x - xx.x	xx.x - xx.x	xx.x - xx.x	xx.x - xx.x
Emergency visit					
N (%)	xx (xx.x)	xx (xx.x)	xx (xx.x)	xx (xx.x)	xx (xx.x)
Mean (std)	xx.x (xx.x)	xx.x (xx.x)	xx.x (xx.x)	xx.x (xx.x)	xx.x (xx.x)
Median	xx.x	xx.x	xx.x	xx.x	xx.x
Q1 - Q3	xx.x - xx.x	xx.x - xx.x	xx.x - xx.x	xx.x - xx.x	xx.x - xx.x
Min - Max	xx.x - xx.x	xx.x - xx.x	xx.x - xx.x	xx.x - xx.x	xx.x - xx.x
Emergency visit (pppm)					
N (%)	xx (xx.x)	xx (xx.x)	xx (xx.x)	xx (xx.x)	xx (xx.x)
Mean (std)	xx.x (xx.x)	xx.x (xx.x)	xx.x (xx.x)	xx.x (xx.x)	xx.x (xx.x)
Median	xx.x	xx.x	xx.x	xx.x	xx.x
Q1 - Q3	xx.x - xx.x	xx.x - xx.x	xx.x - xx.x	xx.x - xx.x	xx.x - xx.x
Min - Max	xx.x - xx.x	xx.x - xx.x	xx.x - xx.x	xx.x - xx.x	xx.x - xx.x
Outpatient physician's visits (private practice, home or outpatient)					
N (%)	xx (xx.x)	xx (xx.x)	xx (xx.x)	xx (xx.x)	xx (xx.x)

	Exposed to OAC			Unexposed to OAC	
	Apixaban (N=XXX)	Dabigatran (N=XXX)	Rivaroxaban (N=XXX)	VKAs (N=XXX)	All exposed (N=XXX)
Mean (std)	xx.x (xx.x)	xx.x (xx.x)	xx.x (xx.x)	xx.x (xx.x)	xx.x (xx.x)
Median	xx.x	xx.x	xx.x	xx.x	xx.x
Q1 - Q3	xx.x - xx.x	xx.x - xx.x	xx.x - xx.x	xx.x - xx.x	xx.x - xx.x
Min - Max	xx.x - xx.x	xx.x - xx.x	xx.x - xx.x	xx.x - xx.x	xx.x - xx.x
Outpatient physician's visits (private practice, home or outpatient) (pppm)					
N (%)	xx (xx.x)	xx (xx.x)	xx (xx.x)	xx (xx.x)	xx (xx.x)
Mean (std)	xx.x (xx.x)	xx.x (xx.x)	xx.x (xx.x)	xx.x (xx.x)	xx.x (xx.x)
Median	xx.x	xx.x	xx.x	xx.x	xx.x
Q1 - Q3	xx.x - xx.x	xx.x - xx.x	xx.x - xx.x	xx.x - xx.x	xx.x - xx.x
Min - Max	xx.x - xx.x	xx.x - xx.x	xx.x - xx.x	xx.x - xx.x	xx.x - xx.x
Outpatient paramedic visits					
N (%)	xx (xx.x)	xx (xx.x)	xx (xx.x)	xx (xx.x)	xx (xx.x)
Mean (std)	xx.x (xx.x)	xx.x (xx.x)	xx.x (xx.x)	xx.x (xx.x)	xx.x (xx.x)
Median	xx.x	xx.x	xx.x	xx.x	xx.x
Q1 - Q3	xx.x - xx.x	xx.x - xx.x	xx.x - xx.x	xx.x - xx.x	xx.x - xx.x
Min - Max	xx.x - xx.x	xx.x - xx.x	xx.x - xx.x	xx.x - xx.x	xx.x - xx.x
Outpatient paramedic visits (pppm)					
N (%)	xx (xx.x)	xx (xx.x)	xx (xx.x)	xx (xx.x)	xx (xx.x)
Mean (std)	xx.x (xx.x)	xx.x (xx.x)	xx.x (xx.x)	xx.x (xx.x)	xx.x (xx.x)
Median	xx.x	xx.x	xx.x	xx.x	xx.x
Q1 - Q3	xx.x - xx.x	xx.x - xx.x	xx.x - xx.x	xx.x - xx.x	xx.x - xx.x
Min - Max	xx.x - xx.x	xx.x - xx.x	xx.x - xx.x	xx.x - xx.x	xx.x - xx.x
Rehabilitation care facilities					
N (%)	xx (xx.x)	xx (xx.x)	xx (xx.x)	xx (xx.x)	xx (xx.x)
Mean (std)	xx.x (xx.x)	xx.x (xx.x)	xx.x (xx.x)	xx.x (xx.x)	xx.x (xx.x)
Median	xx.x	xx.x	xx.x	xx.x	xx.x
Q1 - Q3	xx.x - xx.x	xx.x - xx.x	xx.x - xx.x	xx.x - xx.x	xx.x - xx.x
Min - Max	xx.x - xx.x	xx.x - xx.x	xx.x - xx.x	xx.x - xx.x	xx.x - xx.x
Rehabilitation care facilities (pppm)					
N (%)	xx (xx.x)	xx (xx.x)	xx (xx.x)	xx (xx.x)	xx (xx.x)
Mean (std)	xx.x (xx.x)	xx.x (xx.x)	xx.x (xx.x)	xx.x (xx.x)	xx.x (xx.x)

	Exposed to OAC			Unexposed to OAC	
	Apixaban (N=XXX)	Dabigatran (N=XXX)	Rivaroxaban (N=XXX)	VKAs (N=XXX)	All exposed (N=XXX)
Median	xx.x	xx.x	xx.x	xx.x	xx.x
Q1 - Q3	xx.x - xx.x	xx.x - xx.x	xx.x - xx.x	xx.x - xx.x	xx.x - xx.x
Min - Max	xx.x - xx.x	xx.x - xx.x	xx.x - xx.x	xx.x - xx.x	xx.x - xx.x
Dispensing of observable drugs (AF drugs and other)					
N (%)	xx (xx.x)	xx (xx.x)	xx (xx.x)	xx (xx.x)	xx (xx.x)
Mean (std)	xx.x (xx.x)	xx.x (xx.x)	xx.x (xx.x)	xx.x (xx.x)	xx.x (xx.x)
Median	xx.x	xx.x	xx.x	xx.x	xx.x
Q1 - Q3	xx.x - xx.x	xx.x - xx.x	xx.x - xx.x	xx.x - xx.x	xx.x - xx.x
Min - Max	xx.x - xx.x	xx.x - xx.x	xx.x - xx.x	xx.x - xx.x	xx.x - xx.x
Dispensing of observable drugs (AF drugs and other) (pppm)					
N (%)	xx (xx.x)	xx (xx.x)	xx (xx.x)	xx (xx.x)	xx (xx.x)
Mean (std)	xx.x (xx.x)	xx.x (xx.x)	xx.x (xx.x)	xx.x (xx.x)	xx.x (xx.x)
Median	xx.x	xx.x	xx.x	xx.x	xx.x
Q1 - Q3	xx.x - xx.x	xx.x - xx.x	xx.x - xx.x	xx.x - xx.x	xx.x - xx.x
Min - Max	xx.x - xx.x	xx.x - xx.x	xx.x - xx.x	xx.x - xx.x	xx.x - xx.x
Medication related to AF					
N (%)	xx (xx.x)	xx (xx.x)	xx (xx.x)	xx (xx.x)	xx (xx.x)
Mean (std)	xx.x (xx.x)	xx.x (xx.x)	xx.x (xx.x)	xx.x (xx.x)	xx.x (xx.x)
Median	xx.x	xx.x	xx.x	xx.x	xx.x
Q1 - Q3	xx.x - xx.x	xx.x - xx.x	xx.x - xx.x	xx.x - xx.x	xx.x - xx.x
Min - Max	xx.x - xx.x	xx.x - xx.x	xx.x - xx.x	xx.x - xx.x	xx.x - xx.x
Medication related to AF (pppm)					
N (%)	xx (xx.x)	xx (xx.x)	xx (xx.x)	xx (xx.x)	xx (xx.x)
Mean (std)	xx.x (xx.x)	xx.x (xx.x)	xx.x (xx.x)	xx.x (xx.x)	xx.x (xx.x)
Median	xx.x	xx.x	xx.x	xx.x	xx.x
Q1 - Q3	xx.x - xx.x	xx.x - xx.x	xx.x - xx.x	xx.x - xx.x	xx.x - xx.x
Min - Max	xx.x - xx.x	xx.x - xx.x	xx.x - xx.x	xx.x - xx.x	xx.x - xx.x
Lab tests					
N (%)	xx (xx.x)	xx (xx.x)	xx (xx.x)	xx (xx.x)	xx (xx.x)
Mean (std)	xx.x (xx.x)	xx.x (xx.x)	xx.x (xx.x)	xx.x (xx.x)	xx.x (xx.x)
Median	xx.x	xx.x	xx.x	xx.x	xx.x
Q1 - Q3	xx.x - xx.x	xx.x - xx.x	xx.x - xx.x	xx.x - xx.x	xx.x - xx.x
Min - Max	xx.x - xx.x	xx.x - xx.x	xx.x - xx.x	xx.x - xx.x	xx.x - xx.x

			Exposed to OAC		Unexposed to OAC
	Apixaban (N=XXX)	Dabigatran (N=XXX)	Rivaroxaban (N=XXX)	VKAs (N=XXX)	All exposed (N=XXX)
Lab tests (pppm)					
N (%)	xx (xx.x)	xx (xx.x)	xx (xx.x)	xx (xx.x)	xx (xx.x)
Mean (std)	xx.x (xx.x)	xx.x (xx.x)	xx.x (xx.x)	xx.x (xx.x)	xx.x (xx.x)
Median	xx.x	xx.x	xx.x	xx.x	xx.x
Q1 - Q3	xx.x - xx.x	xx.x - xx.x	xx.x - xx.x	xx.x - xx.x	xx.x - xx.x
Min - Max	xx.x - xx.x	xx.x - xx.x	xx.x - xx.x	xx.x - xx.x	xx.x - xx.x
Medical procedures					
N (%)	xx (xx.x)	xx (xx.x)	xx (xx.x)	xx (xx.x)	xx (xx.x)
Mean (std)	xx.x (xx.x)	xx.x (xx.x)	xx.x (xx.x)	xx.x (xx.x)	xx.x (xx.x)
Median	xx.x	xx.x	xx.x	xx.x	xx.x
Q1 - Q3	xx.x - xx.x	xx.x - xx.x	xx.x - xx.x	xx.x - xx.x	xx.x - xx.x
Min - Max	xx.x - xx.x	xx.x - xx.x	xx.x - xx.x	xx.x - xx.x	xx.x - xx.x
Medical procedures (pppm)					
N (%)	xx (xx.x)	xx (xx.x)	xx (xx.x)	xx (xx.x)	xx (xx.x)
Mean (std)	xx.x (xx.x)	xx.x (xx.x)	xx.x (xx.x)	xx.x (xx.x)	xx.x (xx.x)
Median	xx.x	xx.x	xx.x	xx.x	xx.x
Q1 - Q3	xx.x - xx.x	xx.x - xx.x	xx.x - xx.x	xx.x - xx.x	xx.x - xx.x
Min - Max	xx.x - xx.x	xx.x - xx.x	xx.x - xx.x	xx.x - xx.x	xx.x - xx.x
Medical devices (LPP)					
N (%)	xx (xx.x)	xx (xx.x)	xx (xx.x)	xx (xx.x)	xx (xx.x)
Mean (std)	xx.x (xx.x)	xx.x (xx.x)	xx.x (xx.x)	xx.x (xx.x)	xx.x (xx.x)
Median	xx.x	xx.x	xx.x	xx.x	xx.x
Q1 - Q3	xx.x - xx.x	xx.x - xx.x	xx.x - xx.x	xx.x - xx.x	xx.x - xx.x
Min - Max	xx.x - xx.x	xx.x - xx.x	xx.x - xx.x	xx.x - xx.x	xx.x - xx.x
Medical devices (LPP) (pppm)					
N (%)	xx (xx.x)	xx (xx.x)	xx (xx.x)	xx (xx.x)	xx (xx.x)
Mean (std)	xx.x (xx.x)	xx.x (xx.x)	xx.x (xx.x)	xx.x (xx.x)	xx.x (xx.x)
Median	xx.x	xx.x	xx.x	xx.x	xx.x
Q1 - Q3	xx.x - xx.x	xx.x - xx.x	xx.x - xx.x	xx.x - xx.x	xx.x - xx.x
Min - Max	xx.x - xx.x	xx.x - xx.x	xx.x - xx.x	xx.x - xx.x	xx.x - xx.x
Sickness benefits					
N (%)	xx (xx.x)	xx (xx.x)	xx (xx.x)	xx (xx.x)	xx (xx.x)
Mean (std)	xx.x (xx.x)	xx.x (xx.x)	xx.x (xx.x)	xx.x (xx.x)	xx.x (xx.x)
Median	xx.x	xx.x	xx.x	xx.x	xx.x

			Exposed to OAC		Unexposed to OAC
	Apixaban (N=XXX)	Dabigatran (N=XXX)	Rivaroxaban (N=XXX)	VKAs (N=XXX)	All exposed (N=XXX)
Q1 - Q3	xx.x - xx.x	xx.x - xx.x	xx.x - xx.x	xx.x - xx.x	xx.x - xx.x
Min - Max	xx.x - xx.x	xx.x - xx.x	xx.x - xx.x	xx.x - xx.x	xx.x - xx.x
Sickness benefits (pppm)					
N (%)	xx (xx.x)	xx (xx.x)	xx (xx.x)	xx (xx.x)	xx (xx.x)
Mean (std)	xx.x (xx.x)	xx.x (xx.x)	xx.x (xx.x)	xx.x (xx.x)	xx.x (xx.x)
Median	xx.x	xx.x	xx.x	xx.x	xx.x
Q1 - Q3	xx.x - xx.x	xx.x - xx.x	xx.x - xx.x	xx.x - xx.x	xx.x - xx.x
Min - Max	xx.x - xx.x	xx.x - xx.x	xx.x - xx.x	xx.x - xx.x	xx.x - xx.x
Reimbursed transports					
N (%)	xx (xx.x)	xx (xx.x)	xx (xx.x)	xx (xx.x)	xx (xx.x)
Mean (std)	xx.x (xx.x)	xx.x (xx.x)	xx.x (xx.x)	xx.x (xx.x)	xx.x (xx.x)
Median	xx.x	xx.x	xx.x	xx.x	xx.x
Q1 - Q3	xx.x - xx.x	xx.x - xx.x	xx.x - xx.x	xx.x - xx.x	xx.x - xx.x
Min - Max	xx.x - xx.x	xx.x - xx.x	xx.x - xx.x	xx.x - xx.x	xx.x - xx.x
Reimbursed transports (pppm)					
N (%)	xx (xx.x)	xx (xx.x)	xx (xx.x)	xx (xx.x)	xx (xx.x)
Mean (std)	xx.x (xx.x)	xx.x (xx.x)	xx.x (xx.x)	xx.x (xx.x)	xx.x (xx.x)
Median	xx.x	xx.x	xx.x	xx.x	xx.x
Q1 - Q3	xx.x - xx.x	xx.x - xx.x	xx.x - xx.x	xx.x - xx.x	xx.x - xx.x
Min - Max	xx.x - xx.x	xx.x - xx.x	xx.x - xx.x	xx.x - xx.x	xx.x - xx.x
Total cost in euros (2016-2019) (pppm)					
Total					
Mean (std)	xx.x (xx.x)	xx.x (xx.x)	xx.x (xx.x)	xx.x (xx.x)	xx.x (xx.x)
Median	xx.x	xx.x	xx.x	xx.x	xx.x
Q1 - Q3	xx.x - xx.x	xx.x - xx.x	xx.x - xx.x	xx.x - xx.x	xx.x - xx.x
Min - Max	xx.x - xx.x	xx.x - xx.x	xx.x - xx.x	xx.x - xx.x	xx.x - xx.x
IC 95%	(xx.x - xx.x)	(xx.x - xx.x)	(xx.x - xx.x)	(xx.x - xx.x)	(xx.x - xx.x)
Hospital admission					
n (%)	xx (x.x)	xx (x.x)	xx (x.x)	xx (x.x)	xx (x.x)
Mean (std)	xx.x (xx.x)	xx.x (xx.x)	xx.x (xx.x)	xx.x (xx.x)	xx.x (xx.x)
Median	xx.x	xx.x	xx.x	xx.x	xx.x
Q1 - Q3	xx.x - xx.x	xx.x - xx.x	xx.x - xx.x	xx.x - xx.x	xx.x - xx.x
Min - Max	xx.x - xx.x	xx.x - xx.x	xx.x - xx.x	xx.x - xx.x	xx.x - xx.x
IC 95%	(xx.x - xx.x)	(xx.x - xx.x)	(xx.x - xx.x)	(xx.x - xx.x)	(xx.x - xx.x)

	Exposed to OAC				Unexposed to OAC	
	Apixaban (N=XXX)	Dabigatran (N=XXX)	Rivaroxaban (N=XXX)	VKAs (N=XXX)	All exposed (N=XXX)	Unexposed (N=XXX)
Hospital at home						
n (%)	xx (x.x)	xx (x.x)	xx (x.x)	xx (x.x)	xx (x.x)	xx (x.x)
Mean (std)	xx.x (xx.x)	xx.x (xx.x)	xx.x (xx.x)	xx.x (xx.x)	xx.x (xx.x)	xx.x (xx.x)
Median	xx.x	xx.x	xx.x	xx.x	xx.x	xx.x
Q1 - Q3	xx.x - xx.x	xx.x - xx.x	xx.x - xx.x	xx.x - xx.x	xx.x - xx.x	xx.x - xx.x
Min - Max	xx.x - xx.x	xx.x - xx.x	xx.x - xx.x	xx.x - xx.x	xx.x - xx.x	xx.x - xx.x
IC 95%	(xx.x - xx.x)	(xx.x - xx.x)	(xx.x - xx.x)	(xx.x - xx.x)	(xx.x - xx.x)	(xx.x - xx.x)
Palliative care						
n (%)	xx (x.x)	xx (x.x)	xx (x.x)	xx (x.x)	xx (x.x)	xx (x.x)
Mean (std)	xx.x (xx.x)	xx.x (xx.x)	xx.x (xx.x)	xx.x (xx.x)	xx.x (xx.x)	xx.x (xx.x)
Median	xx.x	xx.x	xx.x	xx.x	xx.x	xx.x
Q1 - Q3	xx.x - xx.x	xx.x - xx.x	xx.x - xx.x	xx.x - xx.x	xx.x - xx.x	xx.x - xx.x
Min - Max	xx.x - xx.x	xx.x - xx.x	xx.x - xx.x	xx.x - xx.x	xx.x - xx.x	xx.x - xx.x
IC 95%	(xx.x - xx.x)	(xx.x - xx.x)	(xx.x - xx.x)	(xx.x - xx.x)	(xx.x - xx.x)	(xx.x - xx.x)
Emergency visit						
n (%)	xx (x.x)	xx (x.x)	xx (x.x)	xx (x.x)	xx (x.x)	xx (x.x)
Mean (std)	xx.x (xx.x)	xx.x (xx.x)	xx.x (xx.x)	xx.x (xx.x)	xx.x (xx.x)	xx.x (xx.x)
Median	xx.x	xx.x	xx.x	xx.x	xx.x	xx.x
Q1 - Q3	xx.x - xx.x	xx.x - xx.x	xx.x - xx.x	xx.x - xx.x	xx.x - xx.x	xx.x - xx.x
Min - Max	xx.x - xx.x	xx.x - xx.x	xx.x - xx.x	xx.x - xx.x	xx.x - xx.x	xx.x - xx.x
IC 95%	(xx.x - xx.x)	(xx.x - xx.x)	(xx.x - xx.x)	(xx.x - xx.x)	(xx.x - xx.x)	(xx.x - xx.x)
Outpatient physician's visits (private practice, home or outpatient)						
n (%)	xx (x.x)	xx (x.x)	xx (x.x)	xx (x.x)	xx (x.x)	xx (x.x)
Mean (std)	xx.x (xx.x)	xx.x (xx.x)	xx.x (xx.x)	xx.x (xx.x)	xx.x (xx.x)	xx.x (xx.x)
Median	xx.x	xx.x	xx.x	xx.x	xx.x	xx.x
Q1 - Q3	xx.x - xx.x	xx.x - xx.x	xx.x - xx.x	xx.x - xx.x	xx.x - xx.x	xx.x - xx.x
Min - Max	xx.x - xx.x	xx.x - xx.x	xx.x - xx.x	xx.x - xx.x	xx.x - xx.x	xx.x - xx.x
IC 95%	(xx.x - xx.x)	(xx.x - xx.x)	(xx.x - xx.x)	(xx.x - xx.x)	(xx.x - xx.x)	(xx.x - xx.x)
Outpatient paramedic visits						
n (%)	xx (x.x)	xx (x.x)	xx (x.x)	xx (x.x)	xx (x.x)	xx (x.x)
Mean (std)	xx.x (xx.x)	xx.x (xx.x)	xx.x (xx.x)	xx.x (xx.x)	xx.x (xx.x)	xx.x (xx.x)
Median	xx.x	xx.x	xx.x	xx.x	xx.x	xx.x
Q1 - Q3	xx.x - xx.x	xx.x - xx.x	xx.x - xx.x	xx.x - xx.x	xx.x - xx.x	xx.x - xx.x

			Exposed to OAC		Unexposed to OAC
	Apixaban (N=XXX)	Dabigatran (N=XXX)	Rivaroxaban (N=XXX)	VKAs (N=XXX)	All exposed (N=XXX)
Min - Max	xx.x - xx.x	xx.x - xx.x	xx.x - xx.x	xx.x - xx.x	xx.x - xx.x
IC 95%	(xx.x - xx.x)	(xx.x - xx.x)	(xx.x - xx.x)	(xx.x - xx.x)	(xx.x - xx.x)
Rehabilitation care facilities					
n (%)	xx (x.x)	xx (x.x)	xx (x.x)	xx (x.x)	xx (x.x)
Mean (std)	xx.x (xx.x)	xx.x (xx.x)	xx.x (xx.x)	xx.x (xx.x)	xx.x (xx.x)
Median	xx.x	xx.x	xx.x	xx.x	xx.x
Q1 - Q3	xx.x - xx.x	xx.x - xx.x	xx.x - xx.x	xx.x - xx.x	xx.x - xx.x
Min - Max	xx.x - xx.x	xx.x - xx.x	xx.x - xx.x	xx.x - xx.x	xx.x - xx.x
IC 95%	(xx.x - xx.x)	(xx.x - xx.x)	(xx.x - xx.x)	(xx.x - xx.x)	(xx.x - xx.x)
Dispensing of observable drugs					
(AF drugs and other)					
n (%)	xx (x.x)	xx (x.x)	xx (x.x)	xx (x.x)	xx (x.x)
Mean (std)	xx.x (xx.x)	xx.x (xx.x)	xx.x (xx.x)	xx.x (xx.x)	xx.x (xx.x)
Median	xx.x	xx.x	xx.x	xx.x	xx.x
Q1 - Q3	xx.x - xx.x	xx.x - xx.x	xx.x - xx.x	xx.x - xx.x	xx.x - xx.x
Min - Max	xx.x - xx.x	xx.x - xx.x	xx.x - xx.x	xx.x - xx.x	xx.x - xx.x
IC 95%	(xx.x - xx.x)	(xx.x - xx.x)	(xx.x - xx.x)	(xx.x - xx.x)	(xx.x - xx.x)
Medication related to AF					
n (%)	xx (x.x)	xx (x.x)	xx (x.x)	xx (x.x)	xx (x.x)
Mean (std)	xx.x (xx.x)	xx.x (xx.x)	xx.x (xx.x)	xx.x (xx.x)	xx.x (xx.x)
Median	xx.x	xx.x	xx.x	xx.x	xx.x
Q1 - Q3	xx.x - xx.x	xx.x - xx.x	xx.x - xx.x	xx.x - xx.x	xx.x - xx.x
Min - Max	xx.x - xx.x	xx.x - xx.x	xx.x - xx.x	xx.x - xx.x	xx.x - xx.x
IC 95%	(xx.x - xx.x)	(xx.x - xx.x)	(xx.x - xx.x)	(xx.x - xx.x)	(xx.x - xx.x)
Lab tests					
n (%)	xx (x.x)	xx (x.x)	xx (x.x)	xx (x.x)	xx (x.x)
Mean (std)	xx.x (xx.x)	xx.x (xx.x)	xx.x (xx.x)	xx.x (xx.x)	xx.x (xx.x)
Median	xx.x	xx.x	xx.x	xx.x	xx.x
Q1 - Q3	xx.x - xx.x	xx.x - xx.x	xx.x - xx.x	xx.x - xx.x	xx.x - xx.x
Min - Max	xx.x - xx.x	xx.x - xx.x	xx.x - xx.x	xx.x - xx.x	xx.x - xx.x
IC 95%	(xx.x - xx.x)	(xx.x - xx.x)	(xx.x - xx.x)	(xx.x - xx.x)	(xx.x - xx.x)
Medical procedures					
n (%)	xx (x.x)	xx (x.x)	xx (x.x)	xx (x.x)	xx (x.x)
Mean (std)	xx.x (xx.x)	xx.x (xx.x)	xx.x (xx.x)	xx.x (xx.x)	xx.x (xx.x)
Median	xx.x	xx.x	xx.x	xx.x	xx.x

	Exposed to OAC			Unexposed to OAC	
	Apixaban (N=XXX)	Dabigatran (N=XXX)	Rivaroxaban (N=XXX)	VKAs (N=XXX)	All exposed (N=XXX)
Q1 - Q3	xx.x - xx.x	xx.x - xx.x	xx.x - xx.x	xx.x - xx.x	xx.x - xx.x
Min - Max	xx.x - xx.x	xx.x - xx.x	xx.x - xx.x	xx.x - xx.x	xx.x - xx.x
IC 95%	(xx.x - xx.x)	(xx.x - xx.x)	(xx.x - xx.x)	(xx.x - xx.x)	(xx.x - xx.x)
Medical devices (LPP)					
n (%)	xx (x.x)	xx (x.x)	xx (x.x)	xx (x.x)	xx (x.x)
Mean (std)	xx.x (xx.x)	xx.x (xx.x)	xx.x (xx.x)	xx.x (xx.x)	xx.x (xx.x)
Median	xx.x	xx.x	xx.x	xx.x	xx.x
Q1 - Q3	xx.x - xx.x	xx.x - xx.x	xx.x - xx.x	xx.x - xx.x	xx.x - xx.x
Min - Max	xx.x - xx.x	xx.x - xx.x	xx.x - xx.x	xx.x - xx.x	xx.x - xx.x
IC 95%	(xx.x - xx.x)	(xx.x - xx.x)	(xx.x - xx.x)	(xx.x - xx.x)	(xx.x - xx.x)
Sickness benefits					
n (%)	xx (x.x)	xx (x.x)	xx (x.x)	xx (x.x)	xx (x.x)
Mean (std)	xx.x (xx.x)	xx.x (xx.x)	xx.x (xx.x)	xx.x (xx.x)	xx.x (xx.x)
Median	xx.x	xx.x	xx.x	xx.x	xx.x
Q1 - Q3	xx.x - xx.x	xx.x - xx.x	xx.x - xx.x	xx.x - xx.x	xx.x - xx.x
Min - Max	xx.x - xx.x	xx.x - xx.x	xx.x - xx.x	xx.x - xx.x	xx.x - xx.x
IC 95%	(xx.x - xx.x)	(xx.x - xx.x)	(xx.x - xx.x)	(xx.x - xx.x)	(xx.x - xx.x)
Reimbursed transports					
n (%)	xx (x.x)	xx (x.x)	xx (x.x)	xx (x.x)	xx (x.x)
Mean (std)	xx.x (xx.x)	xx.x (xx.x)	xx.x (xx.x)	xx.x (xx.x)	xx.x (xx.x)
Median	xx.x	xx.x	xx.x	xx.x	xx.x
Q1 - Q3	xx.x - xx.x	xx.x - xx.x	xx.x - xx.x	xx.x - xx.x	xx.x - xx.x
Min - Max	xx.x - xx.x	xx.x - xx.x	xx.x - xx.x	xx.x - xx.x	xx.x - xx.x
IC 95%	(xx.x - xx.x)	(xx.x - xx.x)	(xx.x - xx.x)	(xx.x - xx.x)	(xx.x - xx.x)

All cost are calculated per patient per month (PPPM)

< Time period >:

6. All: 2016-2019

7. 2016

8. 2017

9. 2017

10. 2018

11. 2019

Table A16. Overall comparison of HCRU and associated cost (during all the follow-up)

	Cost				Anova/Welch test/ Kruskall-Wallis*		Tukey test / Games- Howell test*	
	N (%)	Mean (std)	Median (Q1-Q3)	Min-Max	F	p-value	p-value	Sig**
All cost (2016-2019)								
Total								
Apixaban	xx (x.x)	xx.x (xx.x)	xx.x – xx.x	xx.x – xx.x	x.xx	x.xx	x.xx	ns/*
Dabigatran	xx (x.x)	xx.x (xx.x)	xx.x – xx.x	xx.x – xx.x			x.xx	ns/*
Rivaroxaban	xx (x.x)	xx.x (xx.x)	xx.x – xx.x	xx.x – xx.x			x.xx	ns/*
Unexposed	xx (x.x)	xx.x (xx.x)	xx.x – xx.x	xx.x – xx.x			x.xx	ns/*
VKA (ref)	xx (x.x)	xx.x (xx.x)	xx.x – xx.x	xx.x – xx.x				

All cost is calculated per patient per month (PPPM)

*Test considered depend on verification of the hypothesis

*Post hoc comparisons type of exposure and unexposed vs. VKA (ref) : ***p<0.001, **p<0.01, *p<0.05

3.7. Description of the therapeutic management before/after the first stroke occurring after initiation of OAC therapy

Table A17. Number of occurrences of HCRU 6 and 12 months before and after the first stroke for patients exposed to OAC

	Apixaban (N=XXX)	Dabigatran (N=XXX)	Rivaroxaban (N=XXX)	VKA (N=XXX)	All exposed (N=XXX)
HCRU					
From 12 to 6 months before 1 st stroke date					
n* (%)	xx (x.x)	xx (x.x)	xx (x.x)	xx (x.x)	xx (x.x)
Mean (std)	xx.x (xx.x)	xx.x (xx.x)	xx.x (xx.x)	xx.x (xx.x)	xx.x (xx.x)
Median	xx.x	xx.x	xx.x	xx.x	xx.x
Q1 - Q3	xx.x - xx.x	xx.x - xx.x	xx.x - xx.x	xx.x - xx.x	xx.x - xx.x
Min - Max	xx.x - xx.x	xx.x - xx.x	xx.x - xx.x	xx.x - xx.x	xx.x - xx.x
From 6 months to the 1 st stroke date					
n* (%)	xx (x.x)	xx (x.x)	xx (x.x)	xx (x.x)	xx (x.x)
Mean (std)	xx.x (xx.x)	xx.x (xx.x)	xx.x (xx.x)	xx.x (xx.x)	xx.x (xx.x)
Median	xx.x	xx.x	xx.x	xx.x	xx.x
Q1 - Q3	xx.x - xx.x	xx.x - xx.x	xx.x - xx.x	xx.x - xx.x	xx.x - xx.x
Min - Max	xx.x - xx.x	xx.x - xx.x	xx.x - xx.x	xx.x - xx.x	xx.x - xx.x
From 1 st the stroke date to 6 months after					
n* (%)	xx (x.x)	xx (x.x)	xx (x.x)	xx (x.x)	xx (x.x)
Mean (std)	xx.x (xx.x)	xx.x (xx.x)	xx.x (xx.x)	xx.x (xx.x)	xx.x (xx.x)
Median	xx.x	xx.x	xx.x	xx.x	xx.x
Q1 - Q3	xx.x - xx.x	xx.x - xx.x	xx.x - xx.x	xx.x - xx.x	xx.x - xx.x
Min - Max	xx.x - xx.x	xx.x - xx.x	xx.x - xx.x	xx.x - xx.x	xx.x - xx.x
From 6 to 12 months after the 1 st stroke date					
n* (%)	xx (x.x)	xx (x.x)	xx (x.x)	xx (x.x)	xx (x.x)
Mean (std)	xx.x (xx.x)	xx.x (xx.x)	xx.x (xx.x)	xx.x (xx.x)	xx.x (xx.x)
Median	xx.x	xx.x	xx.x	xx.x	xx.x
Q1 - Q3	xx.x - xx.x	xx.x - xx.x	xx.x - xx.x	xx.x - xx.x	xx.x - xx.x
Min - Max	xx.x - xx.x	xx.x - xx.x	xx.x - xx.x	xx.x - xx.x	xx.x - xx.x
Ambulatory care					
....					
Hospital care					

	Apixaban (N=XXX)	Dabigatran (N=XXX)	Rivaroxaban (N=XXX)	VKA (N=XXX)	All exposed (N=XXX)
--	---------------------	-----------------------	------------------------	----------------	------------------------

....
**Rehabilitation care facilities
(SSR)**
....

....
Medications related to AF
....

*N: number of patients with at least one reimbursement of the specific OAC during the follow-up
 n: represent the number of patients with at least 1 HCRU and at least one reimbursement of specific OAC during the time-period considered

